**HALEON** 

Protocol Number: 300058

### 8.1.5 Inclusion/Exclusion Criteria

Information relating to study inclusion and exclusion criteria will be documented in the app. Individuals who meet the study criteria will be eligible to participate and enrolled into the study.

### 8.2 Study Period

### 8.2.1 Week 0 (Baseline)

Participants must complete the following Baseline activities within 14 days of enrollment to be able to continue in the study.

- Complete DHEQ-48
- Complete NPRS
- Complete OHQ
- Record any changes in their health/medical occurrences; record any changes to their
  existing medications/treatments and any new medications/ treatments (including reason
  for use, unit dose, daily dose, start and stop dates, where known and as appropriate).

Study toothpaste will only be shipped to those participants who complete all 'Baseline' activities. Participants will confirm receipt of their study toothpaste in the confirmation of receipt = Day 0) and will be instructed to start using it on the same day.

### 8.2.2 Weeks 1 and 2

- Complete NPRS
- Record any changes in health/medical occurrences; record any changes to existing
  medications/treatments and any new medications/ treatments (including reason for use,
  unit dose, daily dose, start and stop dates, where known and as appropriate).

### 8.2.3 Weeks 4, 8, 12, 16 and 20

- Complete DHEQ-48
- Complete NPRS
- Record any changes in health/medical occurrences; record any changes to existing
  medications/treatments and any new medications/ treatments (including reason for use,
  unit dose, daily dose, start and stop dates, where known and as appropriate).

### 8.2.4 Week 24

- Complete DHEQ-48
- Complete NPRS
- Complete Treatment Satisfaction NRS
- Record any changes in health/medical occurrences; record any changes to existing
  medications/treatments and any new medications/ treatments (including reason for use,
  unit dose, daily dose, start and stop dates, where known and as appropriate).
- Complete EOS and 'open-ended survey' questions.

Property of Haleon- Confidential

HALEON

8.3 Study Conclusion

The Study Conclusion section of the CCI app will be completed for all participants by virtual site team. If a participant is discontinued early, at any point during the study, the primary reason for withdrawal (if known) should be recorded on the Study Conclusion page.

AEs ongoing at the end of the study will be marked 'unresolved'. CCI medically qualified person (investigator or designee) will ask the participant to seek appropriate medical advice and/or care, as needed. The sponsor will be notified of any ongoing AEs at the end of the study.

# 8.4 SAE Follow-up

will follow-up SAEs until resolution. Follow-up of ongoing SAEs will continue post-study completion and/or after withdrawal or discontinuation will attempt to contact participants with an ongoing SAE at least three times; should the participant continue to be unreachable the SAE will be marked as 'unresolved'.

### 9 STUDY ASSESSMENTS

Every effort should be made to ensure that protocol-required procedures are completed as described in the protocol.

### 9.1 Screening Assessments

Eligibility will be determined against the protocol inclusion/exclusion criteria, based on participant responses to the initial and main screening questionnaire and participant-reported health and medication/treatment information.

# 9.2 Quality of Life (QoL) Assessment

### 9.2.1 Dentin Hypersensitivity Experience Questionnaire (DHEQ-48)

The DHEQ-48 is a condition-specific measure of OHrQoL in relation to DH (Boiko et al, 2010) that has been previously validated in longitudinal studies and shown to be responsive to treatment (Baker et al, 2014). The DHEQ total score can be broken down into 5 separate 'domain' scores to provide a more granular understanding of the specific areas of improvement the participants experience in their OHrQOL.

- **Restrictions:** Derived from participant responses to Section 2, Q1-4 ('the ways in which any sensations in your teeth affect you in your daily life').
- Adaptation: Derived from participant responses to Section 2, Q5-16 ('the ways in which the sensations in your teeth have forced you to change things in your daily life'; 'things you do in your daily life to avoid experiencing the sensations in your teeth').
- **Social Impact:** Derived from participant responses to Section 2, Q17-21 ('the way the sensations affect you when you are with other people or in certain situations').
- **Emotional Impact:** Derived from participant responses to Section 2, Q22-29 ('the way the sensations in your teeth make you feel').

# HALEON

Protocol Number: 300058

• **Identity:** Derived from participant responses to Section 2, Q30-34 ('what the sensations in your teeth mean for you').

The DHEQ also provides specific information on how much the sensations in the participant's teeth affect their life overall:

[figure not shown]
- Global Oral Health: Derived from participant response to Section 2, Q35 ('rate the health of your mouth, teeth and gums').
- Effect on Life Overall: Derived from participant responses to Section 2, Q36-39 (impact of DH on overall QoL).

### 9.3 Safety and Other Assessments

Changes in health and medical occurrences self-reported from immediately after the participant provides e-consent signature until the last use of the study toothpaste will be recorded as AEs; thus, SAEs will also be collected from immediately after the participant provides e-consent signature until last use of the study toothpaste.

### 9.3.1 DH Pain Assessment

Participants will be asked to self-report the intensity of their DH pain at Baseline, 1, 2, 4, 8, 12, 16, 20 & 24 weeks using a Numeric Pain Rating Scale (NPRS). The 11-item NPRS is a segmented numeric version of a Visual Analogue Scale (VAS) from which the respondent selects the score (0–10) that best reflects the intensity of their pain (Hawker et al, 2011; Rocha et al, 2020). Similar to a VAS, the NPRS is anchored by terms describing pain severity extremes. It ranges from '0' representing one pain extreme (e.g., 'no pain') to '10' representing the other pain extreme (e.g., 'worst possible pain'). Higher scores are indicative of greater pain intensity.

At each assessment time point, participants will be asked to record the numeric value on the segmented scale that best describes their pain intensity in the last 24 hours.

[figure not shown]
### 9.3.2 Participant Satisfaction with Treatment

Participants will be asked to rate their satisfaction with the DH treatment using a Numeric Rating Scale (NRS). The NRS is an 11-point ordinal scale used to assess satisfaction with the overall management of the condition for which the individual sought help from treatment. It ranges from 0 (completely dissatisfied) to 10 (completely satisfied), with higher scores indicative of greater satisfaction (van Berckel et al, 2017).

Haleon Clinical Protocol

**HAL**EON

Protocol Number: 300058

Participants will be asked to record the numeric value on the segmented scale that best describes their satisfaction with the DH treatment after 24 weeks of use and indicate why they selected a particular score (e.g., 'Please give more details on why you are satisfied or dissatisfied with the product').

### 9.3.3 Other

On completion of the study (Week 24), participants will be asked to complete a number of EOS/'open-ended survey' questions.

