### 4.4 End of Study Definition

The end of the study is defined for each participant as 168 days ( $\pm$  7days) from the date of confirmation of receipt of study toothpaste (Day 0), participant death, early withdrawal from the study, participant lost to follow-up, or overall study termination.

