# 6.7 Compliance

Participants will be asked to follow the commercial pack usage instructions. To facilitate compliance, the commercial pack app will send study participants weekly notifications/reminders related to product usage (e.g., use the toothpaste every day, follow the usage instructions on the commercial pack), and participants will complete a questionnaire in the app to capture their product usage information.

Participants will be asked to confirm the date of last use of the study product and how many unused tubes of study product remain at the end of the study using the CO app in the EOS/open ended 'survey' questions.

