**HALEON** 

# 7 DISCONTINUATION OF STUDY INTERVENTION AND PARTICIPANT DISCONTINUATION/WITHDRAWAL

# 7.1 Participant Discontinuation/Withdrawal

Participants may withdraw from the study at any time at their own request. Their right to withdraw and information about how to withdraw will be included in the eIC. Should a participant withdraw or be discontinued from the study, all further scheduled communication with that participant will be discontinued (e-mails, text messages, and/or notifications). The reason(s) for withdrawal or discontinuation will be recorded in the CCI portal.

If the participant withdraws from the study and withdraws consent for disclosure of future information, no additional data will be collected. The sponsor may retain and continue to use data collected before the withdrawal of consent.

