4.3.2 Data Display

In general, all data will be listed by subject and visit/time point where appropriate. The total number of subjects under the stated population (N) will be displayed in the header of summary tables.

Data will be summarized using descriptive statistics for continuous variables. Unless otherwise specified, descriptive statistics will include number of subjects, mean, standard deviation, standard error, minimum, median, and maximum. The minimum and maximum statistics will be presented to the same number of decimal places as the original data. The mean and median will be presented to one more decimal place than the original data, whereas the standard deviation and standard error will be presented to two more decimal places than the original data.

In summary tables of categorical variables, counts and percentages will be used. Descriptive summaries of categorical endpoints will include counts (missing and non-missing) and percentage (%) out of the participants with non-missing data.

P-values will be displayed with 4 decimals, e.g., p=0.0001 and p-values below 0.0001 will be displayed as p<0.0001.

In by-visit summary tables only scheduled visits/timepoints will be summarized. In listings, all visits and timepoints with any data collected will be included.

The change from baseline values will be derived for each subject as the post-baseline evaluation minus the baseline evaluation.

All dates will be displayed in ISO 8601 date format (YYYY-MM-DD).

Residual analyses will be conducted for each MMRM applied.

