4.3.7 Compliance

Study product compliance and compliance to the study schedule will be tabulated and summarized for the safety population.

Summaries will include a simple yes/no frequency (and percent) count at each timepoint:

- Summary of completion to each study schedule and assessments (yes/no)
- Summary of product usage according to product instructions (more than 5 days/5 days or fewer)
- Summary of number of tubes remaining at the end of the study (number remaining) into three categories: 2 or less tubes, 3 to 6 tubes, and more than 6 tubes.

A listing of number of tubes remaining per subject will also be produced for the safety population.

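### Unused tubes and date of last use are asked only at Week 24, so the tubes-remaining table labelled Safety population describes Week 24 responders and probably overstates use

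*Protocol*

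**What the plan says.** Protocol 6.7 sets the two product-accounting items: "Participants will be asked to confirm the date of last use of the study product and how many unused tubes of study product remain". It places them in the end-of-study (EOS) and open-ended survey questions, and Table 6-1 does the same for the tube count. Table 1-1 and 8.2.4 schedule those questions at Week 24 alone, and 9.3.3 agrees: "On completion of the study (Week 24), participants will be asked to complete a number of" EOS questions.

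For people who leave early, Protocol 4.4 lists among the events that end a participant's study "early withdrawal from the study, participant lost to follow-up, or overall study termination". At withdrawal or discontinuation, 7.1 says that "all further scheduled communication with that participant will be discontinued". The only exit item that 8.3 describes for them is that "the primary reason for withdrawal (if known) should be recorded on the Study Conclusion page". Section 8 blocks entries made outside a visit window.

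On analysis, SAP 4.3.7 states: "Study product compliance and compliance to the study schedule will be tabulated and summarized for the safety population". It plans three summaries: completion of schedule and assessments, product usage, and tubes remaining in three classes (2 or fewer, 3 to 6, more than 6). Protocol 12.3.5.1 plans the same three topics. The general rule in SAP 4.3.2, also in Protocol 12.3, is to show missing and non-missing counts with "percentage (%) out of the participants with non-missing data".

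**The concern.** The tube table carries a Safety population label, but its percentages can come only from people who answered at Week 24. The missing people are not a neutral subset. All 12 tubes are sent in one carton, so someone who stops early has had less time to use them and is more likely to have many left. The class that signals low use is the one that loses members.

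Two things are at stake. The primary objective concerns change over 24 weeks of use, and the tube count is part of the planned evidence on how far the product was used. The date of last use also has a role outside the compliance tables: it closes collection of adverse events (Table 1-1 footnote 4, 9.3, 10.3), concomitant medications (6.8) and pregnancies (10.9). If it is not asked at exit, it cannot be recovered at analysis.

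**Working it through.** **Route to the data.** Both items are EOS items, and EOS is scheduled at Week 24 only. Scheduled contact stops at withdrawal, late entry is blocked, and the exit record is described only as holding the reason for leaving. Early leavers therefore have no planned route to report either item. The SAE form (10.4.2) lists a product end date as desirable, but it exists only for participants with an SAE.

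**Denominator.** SAP 4.3.7 sets no rule of its own, so the non-missing rule of 4.3.2 applies. SAP 4.3.5 does fix a denominator, the number enrolled, for disposition. SAP 4.3.15 gives missing-data handling for the DHEQ and the MMRM, not for compliance.

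**The plan's own figure.** 400 / (1 − 0.20) = 500, which reproduces the stated 500 enrolled and 400 completing. At that maximum dropout the tube percentages rest on 400/500 = 80% of participants.

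**Direction.** If 12 tubes are to last 24 weeks, use is at most 12/24 = 0.5 tube per week on average. At that rate, tubes left at week w are 12 − 0.5w, which exceeds 6 for w < 12. If only unopened tubes count, those left are 12 minus w/2 rounded up, which exceeds 6 up to about Week 10. Either way, early stoppers fall mainly in the top class.

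**Size.** Let m be the share with no Week 24 answer, p the share of responders with more than 6 tubes left, and q that share among the rest. The table shows p; the full-population share is (1 − m)p + mq; the understatement is m(q − p). From the documents: 500, 400, up to 20%, 12 tubes. Assumed: all 500 used the product, p = 10%, and q = 30%, 50% or 80%.

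| m | Table shows | q = 30% | q = 50% | q = 80% |
|---|---|---|---|---|
| 20% | 10% | (40+30)/500 = 14% | (40+50)/500 = 18% | (40+80)/500 = 24% |
| 10% | 10% | (45+15)/500 = 12% | (45+25)/500 = 14% | (45+40)/500 = 17% |
| 5% | 10% | 10% + 0.05 × 20 points = 11% | 10% + 0.05 × 40 points = 12% | 10% + 0.05 × 70 points = 13.5% |

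The sign reverses only if q < p, that is, if leavers have fewer tubes left than responders.

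**What a reader could recover.** With 40/400, 100 missing and N = 500 displayed, the bounds for the class are 40/500 = 8% and (40+100)/500 = 28%. The headline 10% lies near the lower end.

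**The case against.** The strongest reply is that the effect is confined to one descriptive table and the plan already discloses the gap. Most of this stands.

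- A reader might infer that all the compliance tables describe Week 24 responders. They do not. Usage comes from an in-app questionnaire and brushing diary (Protocol 6.7; SAP 4.3.3, 4.3.14), and both usage and schedule completion are tabulated by timepoint. Usage percentages also lose non-responders at later timepoints, but do not depend on the EOS survey. No planned compliance table uses the last-use date.
- Missing counts are planned and N appears in each table header (SAP 4.3.2), so the bounds can be recomputed. This reveals the gap but does not supply the missing answers.
- Not everyone who falls silent is lost. Reminders continue to Week 24 plus 7 days (7.2) and app access stays open (Section 8), so a silent participant can still answer at Week 24. The lack of a route applies to those who withdraw or are discontinued.
- A reader might infer that usage compliance is shown to be overstated, for example 380/400 = 95% among responders against 380/500 = 76% overall. The 76% counts every unknown as non-use. The bounds run to (380+100)/500 = 96%, so 95% lies inside them. Leaving the study is also not the same as stopping the product, which participants may keep (Table 6-1).
- A reader might infer that DHEQ change cannot be related to use for early leavers. First use is confirmed in the app (6.2) and diary data are listed per participant, so exposure to the last entry is available. No such analysis is planned, and compliance does not enter the MMRM.
- The 20% is an upper planning figure counted from enrolment. Enrolled people who never use the product are outside the Safety population, so the missing share there may be smaller.
- Table 6-1 defines the count at the end of the 24-week treatment period. A count at an early exit also reflects time in study, which is a reason to show it separately.

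**Conclusion.** The point holds for the tube count and the last-use date. The tubes-remaining percentages labelled Safety population cover Week 24 responders only, about 80% of participants at the planned maximum dropout. They probably understate the class with more than 6 tubes left, and so overstate use. On the stated assumptions the table shows 10% against 14% to 24% at 20% missing, and the gap shrinks in proportion to the missing share. The direction rests on leavers having more tubes left than responders, which is likely but not certain; the documents do not give the rates that set the size. Separately, no scheduled item captures for early leavers the date that closes the adverse-event, concomitant-medication and pregnancy windows. The primary MMRM is unaffected.

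**What to change.** 1. Protocol 6.7 and 8.3, with a footnote to Table 1-1: at early discontinuation, ask for the date of last use and the number of unused tubes as optional items, at the discontinuation contact itself because scheduled communication then stops. This brings product accounting into line with the 4.4 definition of end of study.
2. SAP 4.3.7 and Protocol 12.3.5.1: give tube and usage percentages on the Safety population N, with a row for not reported or left the study. For tubes, show completers and early leavers separately.
3. Optionally, summarise duration of use from first-use confirmation to last use, or to the last diary entry where last use is missing.

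The cost is two short questions, some SAP wording and one table row, with no extra participants or visits. The compliance figure will look less favourable, and some leavers will not answer. Item 2 can be done at analysis; item 1 works only if it is in place before participants leave.

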### 10 ADVERSE EVENT AND SERIOUS ADVERSE EVENTS

is responsible for detecting, documenting, and reporting events that meet the definition of an AE or SAE, and for following up AEs that are serious (SAEs), considered related to either the study product or study participation, or that caused the participant to discontinue use of the study product or study participation.

### 10.1 Definition of an Adverse Event (AE)

An AE is any untoward medical occurrence in a study participant, temporally associated with the use of a study product, whether or not considered related to the study product.

**Note:** An AE can therefore be any unfavorable and unintended sign (including an abnormal laboratory finding), symptom, or disease (new or exacerbated) temporally associated with the use of a study product.

### **Events Meeting the AE Definition:**

- Any abnormal laboratory test results (hematology, clinical chemistry, or urinalysis) or
  other safety assessments (e.g., ECG, radiological scans, vital sign measurements),
  including those that worsen from baseline, considered clinically significant in the
  medical and scientific judgment of the investigator/CCI medically qualified
  person (i.e., not related to progression of underlying disease).
- Exacerbation of a chronic or intermittent pre-existing condition including either an increase in frequency and/or intensity of the condition.
- New conditions detected or diagnosed after study product usage even though it may have been present before the start of the study.
- Signs, symptoms, or the clinical sequelae of a suspected drug-drug interaction.

Property of Haleon- Confidential

May not be used, divulged, published or otherwise disclosed without the consent of Haleon

HALEON

Signs, symptoms, or the clinical sequelae of a suspected overdose of either study product
or a concomitant medication. Overdose per se will not be reported as an AE/SAE unless
it is an intentional overdose taken with possible suicidal/self-harming intent. Such
overdoses should be reported regardless of sequelae.

### Events **NOT** meeting the AE definition:

- Any clinically significant abnormal laboratory findings (if applicable) or other abnormal safety assessments which are associated with the underlying disease, unless judged by the investigator/ medically qualified person to be more severe than expected for the participant's condition.
- The disease/disorder being studied or expected progression, signs, or symptoms of the disease/disorder being studied, unless more severe than expected for the participant's condition.
- Medical or surgical procedure (e.g., endoscopy, appendectomy) is not the AE. The
  condition that leads to the procedure is an AE (e.g., appendicitis).
- Situations where an untoward medical occurrence did not occur (social and/or convenience admission to a hospital).
- Anticipated day-to-day fluctuations of pre-existing disease(s) or condition(s) present or detected at the start of the study that do not worsen.

# 10.2 Definition of a Serious Adverse Event (SAE)

A serious adverse event (SAE) is a particular category of an adverse event where the adverse outcome is serious. If an event is not an AE per definition above, then it cannot be an SAE, even if serious conditions are met (e.g., hospitalization for signs/symptoms of the disease under study, death due to progression of disease).

A serious adverse event is any untoward medical occurrence at any dose that:

### Results in death

### Is life-threatening

- The term 'life-threatening' in the definition of 'serious' refers to an event in which the participant was at risk of death at the time of the event. It does not refer to an event, which hypothetically might have caused death, if it were more severe.

### Requires in-patient hospitalization or prolongation of existing hospitalization

- In general, hospitalization signifies the participant has been detained (usually involving at least an overnight stay) at the hospital or emergency ward for observation and/or treatment that would not have been appropriate in the physician's office or outpatient setting. Complications that occur during hospitalization are AEs. If a complication prolongs hospitalization or fulfills any other serious criteria, the event is serious. When in doubt as to whether 'hospitalization' occurred, or was necessary, the AE should be considered serious.
- Hospitalization for elective treatment of a pre-existing condition that did not worsen from baseline is not considered an AE.

